Appendix C Examples of SAS code

Table 11: SAS code for primary efficacy analysis

SAS code
proc mixed data= method=reml plots=studentpanel(marginal conditional); class treatment cohort age_group pollen_station; model TCS_sqrt= treatment cohort age_group / ddfm = KenwardRogers residual; random pollen_station (cohort); repeated/group=treatment; lsmeans treatment / cl cov diff; run;

TCS_{sqrt} is the square root of the average TCS.

Table 12: Example for calculating proportion endpoints

SAS code
proc glimmix data =; class treatment cohort age_group pollen_station; model aval / datadays = treatment cohort agegroup / dist=binomial link=logit; random pollen_station(cohort); lsmeans treatment / diff ilink oddsratio cl; run;

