15.12.6 Secondary efficacy analyses

The following secondary endpoints will be analysed identically to the primary endpoint using the estimators of the trial product and treatment policy estimands: average TCS, average DSS and average DMS during the AHPS and OPS, average TCS (EAACI scoring)

Proportion of severe days, proportion of well days, proportion of symptom-free days and patientrated global evaluation of treatment efficacy (categorised as improvement versus no improvement) will be analysed with a logistic regression model with treatment, pollen season and age group as fixed effects and pollen station (or region) as random effects.

Average weekly overall RQLQ scores during the BPS and TPS, overall PRQLQ scores during the BPS and TSQM-9 domain scores will be analysed with a linear mixed model.

Change from baseline in immunological endpoints will be analysed with a repeated measures linear mixed model.

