15.15 Handling of missing data and sensitivity analyses

Efficacy endpoints which are an average of daily diary entries over a defined pollen season will be derived provided there is at least one relevant diary entry for that endpoint in the given pollen season. Subjects with missing data for an endpoint will be included in the analysis of that endpoint through multiple imputation (see Sections **15.12.2**, **15.12.3** and **15.12.4**). Detailed specification of sensitivity analyses to address the assumptions underlying the main estimators of each estimand will be provided in the SAP.

Imputation of missing daily diary data is not considered for the main estimators of the trial product and treatment policy estimands. Occasional missing diary values are assumed to be missing completely at random (MCAR) and are therefore not a source of bias in the derivation of the endpoints. Investigation of patterns of extended periods of missing daily diary data and potential sensitivity analyses, however, will be considered in the SAP although appropriate imputation of missing daily diary values is a complex problem. Diary entries over the course of a pollen season are highly specific to the subject completing the diary; they are a function of the local pollen exposure in the immediate environment of the subject and that individual subject's tolerance to allergic rhinoconjunctivitis symptoms and subsequent rescue medication usage. Imputation of missing daily data could easily introduce daily data inconsistent with a subject's individual profile and subsequent bias in the derivation of the endpoints.

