4.1.1 Multiplicity adjustment

For the trial product estimand based on the primary efficacy endpoint and the key secondary efficacy endpoints, the analyses for the main estimators will be controlled for multiplicity to ensure a maximum overall type I error rate of 5% in the hypothesis testing of these endpoints.

The control for multiplicity will be performed through hierarchical testing, using a pre-specified order of hypothesis to be tested. For each endpoint, the null hypothesis to be tested is the hypothesis of no difference between placebo and active SQ tree SLIT-tablet. Let μ_1 denote the mean in the SQ tree SLIT-tablet group, and μ_2 denote the mean in the placebo group. Then the null hypothesis (H_0) and the alternative hypothesis (H_A) are given as follows:

$$H_0: \mu_1 = \mu_2 \text{ and } H_A: \mu_1 \neq \mu_2$$

The order of the hypotheses to be tested is:

1. The primary efficacy analysis of average TCS during BPS
2. The key secondary efficacy analysis of average TCS during TPS
3. The key secondary efficacy analysis of average DSS during BPS
4. The key secondary efficacy analysis of average DSS during TPS
5. The key secondary efficacy analysis of average DMS during BPS
6. The key secondary efficacy analysis of average DMS during TPS

The first hypothesis in the hierarchy will be tested at a two-sided 5% significance level. Testing will proceed to the second hypothesis only if the first test is statistically significant ($p < 0.05$). Similarly, testing will proceed to the next level of the hierarchy, only if the previous comparison is statistically significant at the 5% level. If a test is not statistically significant ($p > 0.05$) then no further testing within the hierarchy will be conducted. Thus, the 2nd, 3rd, 4th, 5th, and 6th hypothesis tests in the hierarchy will only be conducted if all previously tested hypotheses are statistically significant at the 5% level.

Furthermore, analysis of the quality of life endpoints will be included as the final steps in the testing hierarchy, where the order of the hypotheses to be tested is:

7. The secondary efficacy analysis of average weekly overall RQLQ score during the BPS
8. The secondary efficacy analysis of average weekly overall RQLQ score during the TPS
9. The secondary efficacy analysis of overall PRQLQ score during the BPS

Additional endpoints and analyses are supportive in nature and are not controlled for multiplicity.

5 Analysis sets

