6.6 Additional endpoints analyses

6.7 Secondary endpoints

The following secondary endpoints will be analysed identically to the primary endpoint using the main estimator for the trial product estimand:

- Average TCS during the AHPS and OPS
- Average DSS during the AHPS and OPS
- Average DMS during the AHPS and OPS
- Average TCS (EAACI scoring) during BPS and TPS

Following endpoints will be analysed under the hypothetical strategy using the same intercurrent events and imputation approach defined for the main estimator.

- Proportion of severe days during BPS and TPS
- Proportion of well days during BPS and TPS
- Proportion of symptom-free days during BPS and TPS

The proportion of severe days during BPS will be analysed using a GLMM with a logit link function. For the proportion of severe days during BPS the model will include “number of severe days/total number of days in BPS” as the response variable and treatment, cohort and age group as fixed effects and pollen station within cohort as random effects. From the GLMM model, the odds ratio of having a severe day of active treatment relative to placebo will be presented together with the corresponding p-values and 95% confidence limits. The endpoints proportion of severe days during TPS, proportion of well days during BPS and TPS, and symptom-free days during BPS and TPS will be analysed using the same model as for severe days during BPS. The imputation of missing data of aforementioned endpoints, will be done by using unrestricted random sampling method, which utilises selection with equal probability and with replacement. For each subject with missing data, the number of days in pollen season as well as the number of days with the endpoint of interest will be replaced from the pool of completed subjects with non-missing data in the same age group and the treatment group according to hypothetical strategy.

A plot with the results from the statistical analyses of the endpoints proportion of severe days, proportion of well days and proportion of symptom-free days during BPS will be presented. The plot will include estimated proportions of having a severe day, well day and symptom free days, the relative difference including 95% CI, and a p-values.

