9.2.3 Derivation of daily binary variables

9.2.3.1 Proportion of well days

A well day is defined as a day with no use of AR/C rescue medication (i.e., DMS=0) and DSS less than or equal to 2. A day that meets the definition of well day will take the value 1, and 0 otherwise.

The proportion of well days during BPS and TPS is the number of well days/total number of days in a season (BPS or TPS).

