9.2.3.2 Proportion of severe days

[figure not shown]
A severe day is a day with a DSS greater than or equal to 6 and at least 2 moderate symptoms or 1 severe symptom. A day that meets the definition of severe day will take the value 1, and 0 otherwise.

The proportion of severe days during BPS and TPS is the number of severe days/total number of days in a season (BPS or TPS).

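### The severe-, well- and symptom-free-day models ignore correlation between a child's diary days, so their standard errors are too small, and the denominator differs between text and code

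*SAP*

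**What the plan says.** SAP 6.7 analyses the number of severe days over the number of days in the BPS with a logit-link GLMM, taking this ratio "as the response variable and treatment, cohort and age group as fixed effects and pollen station within cohort as random effects". The other five endpoint-season combinations use the same model: severe days in the TPS, and well and symptom-free days in both seasons. Each yields an odds ratio, p-value and 95% confidence limits. The three BPS results are also plotted (SAP 6.7: "proportion of well days and proportion of symptom-free days during BPS will be presented").

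The code in SAP Table 12 matches on effects: "model aval / datadays = treatment cohort agegroup / dist=binomial link=logit; random pollen_station(cohort". Protocol 15.12.6 likewise has a "logistic regression model with treatment, pollen season and age group as fixed effects and pollen station (or region) as random effects".

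On the denominator, SAP 9.2.3.2 states: "The proportion of severe days during BPS and TPS is the number of severe days/total number of days in a season (BPS or TPS". SAP 9.2.3.1 and 9.2.3.3 use the same form for well and symptom-free days. Table 12 divides by `datadays`, which the SAP does not define. SAP 9.2.3.1 adds: "A day that meets the definition of well day will take the value 1, and 0 otherwise". It does not say how a day without a diary entry is coded.

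**The concern.** Each child contributes one record: a count of event days out of several weeks of days. A binomial likelihood gives that count the variance it would have if the days were independent at a common probability, given station, treatment, cohort and age group. Protocol 15.15 says otherwise: "Diary entries over the course of a pollen season are highly specific to the subject completing the diary". Children at the same station differ in sensitivity, exposure and rescue use, so the counts vary more between children than the binomial allows.

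The station effect cannot absorb this, because children at one station are randomised to both arms. Rubin's rule adds variance only for imputed children. SAP 6.7.2 does include a subject effect for the repeated immunology measurements, so the omission here looks unintended.

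The denominator raises a separate problem. If the season length is the divisor and days without an entry score 0, missing days count as neither severe nor well. The same would happen to days removed after treatment discontinuation under the hypothetical strategy. The average-score endpoints in SAP 9.2.2 use non-missing days only, so the two families of endpoints would treat missing days differently.

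**Working it through.** **The plan's own figures.** The documents state no power, ICC or variance for these endpoints. Their only power table concerns the primary endpoint, and it reproduces. On the square-root scale the difference is 2.5 × (1 − √0.7625) = 0.317 for the FAS and 2.5 × (1 − √0.75) = 0.335 for observed cases. With SD 1.4 and 500 or 450 per arm, power is 94.7% (stated 95.0%) and 94.8% (stated 94.7%).

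**Days per child.** From SAP Appendix D, the BPS averages 27.6 days over 65 station-seasons (range 4–47). The TPS, taken as the union of hazel, alder, birch and oak days, averages 86.5 days over 66 station-seasons (median 90.5).

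**Formula.** With m days per child, the true variance of the treatment log odds ratio is about DE = 1 + (m − 1) × ICC times the model variance. The true type I error of a nominal two-sided 5% test is 2 × (1 − Φ(1.96/√DE)). For the BPS at ICC 0.1, DE = 1 + 26.6 × 0.1 = 3.66, √DE = 1.91 and 1.96/1.91 = 1.02, giving 31%.

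**Simulation.** The Table 12 model was also simulated under no treatment effect, with 1,500 trials per scenario. The simulation assumed 1,000 subjects spread evenly over station-seasons, 1:1 allocation within station, a 25% event rate, station SD 0.5 on the logit scale and beta-binomial children.

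| Assumed ICC | BPS, formula | BPS, simulated | TPS, formula | TPS, simulated |
|---|---|---|---|---|
| 0 | 5% | 6% | 5% | 7% |
| 0.05 | 20% | 21% | 39% | 45% |
| 0.1 | 31% | 34% | 53% | 55% |
| 0.5 | 60% | 62% | 77% | 79% |

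In the simulation the mean odds ratio stays at 1.00. Reported standard errors are too small by factors of 1.6, 2.0 and 4.1 (BPS) and 2.4, 3.4 and 7.2 (TPS) at ICC 0.05, 0.1 and 0.5. At ICC 0.1, an event rate of 10% or a station SD of 1.0 changes little: 33–34% for the BPS and 54–55% for the TPS.

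A separate, smaller null simulation used logit-normal children, fixed station effects and BPS lengths (150 runs per setting). Type I error was 4–6% with no child-level variance, and 13–19%, 33–43% and 53–59% at child-level logit SD 0.5, 1 and 2.

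**How small must the ICC be?** Type I error reaches 10% when 1.96/√DE = 1.645, so DE = 1.42. That gives ICC = 0.42/26.6 = 0.016 (BPS) and 0.42/85.5 = 0.005 (TPS).

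**Is an ICC that small plausible?** SAP section 7 assumes that the square root of the average TCS has mean 2.5 and SD 1.4.
- Under normality, the average TCS has mean 2.5² + 1.4² = 8.21 and variance 4 × 2.5² × 1.4² + 2 × 1.4⁴ = 56.7.
- Daily TCS lies between 0 and 38, so its variance cannot exceed 8.21 × (38 − 8.21) = 244.6.
- Solving 56.7/244.6 = ICC + (1 − ICC)/27.6 gives an ICC of at least 0.20.
- If half of the 56.7 were between stations (an assumption), 28.3/244.6 gives about 0.08, and a type I error of about 27%.

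This bound concerns daily TCS, not the binary indicators. They are built from the same diary items, however, and a symptom-free day is exactly a day with TCS 0.

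**Denominator, read literally.** At 80% completeness a true 30% of well days is reported as 0.30 × 0.80 = 24%. Equal completeness in the arms leaves a null odds ratio at 1.00. With an assumed 80% against 85%:
- severe days (true rate 25%): odds(0.200)/odds(0.2125) = 0.250/0.270 = 0.93;
- well days (true rate 30%): odds(0.240)/odds(0.255) = 0.316/0.342 = 0.92.

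The less complete arm thus looks better on severe days and worse on well and symptom-free days.

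**The case against.** The strongest objection is that little depends on these analyses. They lie outside the nine-step hierarchy, and SAP 4.1.1 says: "Additional endpoints and analyses are supportive in nature and are not controlled for multiplicity". That stands, and it limits the consequence to the intervals and p-values of supportive results.

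Next, no ICC can be taken from the documents, so only the direction of the error is firm. The figures at ICC 0.5 in particular are assumptions, as labelled.

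The TPS figures may also run high. Diary compliance is aimed only at 80% or more (protocol 14.2), and recording starts at the expected season start, while Appendix D lists actual seasons. With 0.8 × 86.5 = 69.2 days the formula gives 35%, 48% and 74% in place of 39%, 53% and 77%. Correlation that decays over a long, interrupted season would lower them further. The simulated 7% at ICC 0 shows a small excess of the simulation's own, and the simulation omits multiple imputation. None of this removes the inflation.

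On the denominator, Table 12 is headed as an example, scoring days without an entry as 0 is one reading and not a stated rule, and the unequal completeness is hypothetical. SAP 6.9.1.4 summarises eDiary compliance by arm over the TPS, so an imbalance there would be visible. What stands is that text and code differ and `datadays` is undefined. The example heading does not excuse the correlation problem, because the text of SAP 6.7 specifies the same model.

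**Conclusion.** The concern holds. Followed as written, the plan gives standard errors that are too small, intervals that are too narrow and p-values that are too low in six reported analyses: three endpoints in two seasons. The direction needs only positive within-child correlation, which protocol 15.15 implies. The size depends on an ICC that the documents do not give; type I error exceeds 10% from an ICC of about 0.016 (BPS) or 0.005 (TPS).

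The odds ratio is not grossly biased by this. The primary, key secondary and quality-of-life tests are unaffected, as is the global evaluation, which has one response per child.

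The denominator is an inconsistency to reconcile. It biases the comparison only if season days are the divisor, missing days score 0 and completeness differs between arms.

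**What to change.** In SAP 6.7 and Table 12, allow for within-child correlation. The simplest change is a residual overdispersion scale (`random _residual_`), which keeps the planned odds ratio conditional on station. A beta-binomial model or subject-clustered robust standard errors would also serve. A subject random intercept is possible but changes the odds ratio to a subject-specific one.

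In the simulation of the Table 12 model, the residual scale brought type I error to 5.5–7.0% (BPS) and 5.9–8.3% (TPS). That is close to the 6–7% the planned model shows with no within-child correlation. Clustered standard errors, checked with station as fixed effects (600 trials per scenario), gave 2.8–7.3%. Neither is exact, but both remove most of the inflation.

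In SAP 6.7, 9.2.3.1–9.2.3.3 and Table 12, define `datadays` once as days in the season with non-missing diary data, restricted to on-treatment days where DPS1 applies. This matches the average scores. Table 12 should also use one name for age group, since `age_group` in the class statement becomes `agegroup` in the model.

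The cost is one code statement, one sentence in 6.7 and the denominator wording. Data collection does not change. The downside is wider intervals.

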Appendix D Final pollen season

pollen_station	Season	Cohort	Start_date	End_date	Average grains/m3	Neighbouring	comments
ATWIEN	ALDER	1	05-02-2022	30-03-2022	95,6		
CZTRIN	ALDER	1	13-02-2022	30-03-2022	110,1		
DEAACH	ALDER	1	09-02-2022	08-03-2022	47		
DEBOCH	ALDER	1	07-02-2022	13-03-2022	54,7		
DEBORS	ALDER	1	27-01-2022	25-03-2022	109,8		
DEDRES	ALDER	1	12-02-2022	24-03-2022	55		
DELEVE	ALDER	1	07-02-2022	13-03-2022	27,2		
DELOEW	ALDER	1	04-02-2022	22-03-2022	52,8		
DEMARB	ALDER	1	08-02-2022	23-03-2022	64,7		
DEMOEN	ALDER	1	07-02-2022	13-03-2022	34,7		
DKCOPE	ALDER	1	12-02-2022	15-03-2022	20		
FRSTRA	ALDER	1	02-02-2022	28-03-2022	324,8		
HUGYOE	ALDER	1	03-02-2022	26-03-2022	84,7		
HUMISK	ALDER	1	05-02-2022	01-05-2022	36,3		
HUPEST	ALDER	1	04-02-2022	30-03-2022	118,2		
HUSALG	ALDER	1	05-02-2022	03-04-2022	107,4		
HUSZE2	ALDER	1	15-02-2022	29-03-2022	65,2		
LTSIAU	ALDER	1	24-02-2022	28-03-2022	82,3		
LTVILN	ALDER	1	25-02-2022	05-04-2022	63,5		
PLBYDG	ALDER	1	13-02-2022	06-04-2022	171,7		
PLCRAC	ALDER	1	13-02-2022	28-03-2022	156,3		
PLKATO	ALDER	1	08-02-2022	04-04-2022	126,5		
PLLODZ	ALDER	1	13-02-2022	02-04-2022	180,8		
PLLUBL	ALDER	1	15-02-2022	29-03-2022	120,6		
PLPTRY	ALDER	1	08-02-2022	05-04-2022	175,1		
PLSZCZ	ALDER	1	05-02-2022	14-03-2022	51,5		
RUMOSC	ALDER	1	14-03-2022	12-04-2022			
SKBRAT	ALDER	1	09-02-2022	09-04-2022	113,6		
ATWIEN	ALDER	2	20-02-2023	11-03-2023	19,3		
BEBRUS	ALDER	2	08-02-2023	23-03-2023	133,4	NLLEID	completely missing
BEMARC	ALDER	2	07-02-2023	24-03-2023	153,8	DEMOEN	completely missing
CZTRIN	ALDER	2	07-03-2023	10-03-2023	27,5		
DEBOCH	ALDER	2	13-02-2023	22-03-2023	141,2		
DEDRES	ALDER	2	16-02-2023	03-03-2023	71,8		
DELEVE	ALDER	2	07-02-2023	24-03-2023	153,8	DEMOEN	partially missing
DELIPP	ALDER	2	16-02-2023	21-03-2023	83,1		

DELOEW	ALDER	2	15-02-2023	06-03-2023	76,5		
DEMARB	ALDER	2	22-02-2023	18-03-2023	63,4		
DEMOEN	ALDER	2	07-02-2023	24-03-2023	153,8		
DEMUNC	ALDER	2	16-02-2023	10-03-2023	38		
DKCOPE	ALDER	2	11-02-2023	03-04-2023	41,8		
DKVIBO	ALDER	2	01-03-2023	03-04-2023	12,8		
FRSTRA	ALDER	2	02-02-2023	14-03-2023	127,7		
HUGYOE	ALDER	2	17-02-2023	10-03-2023	45,3		
HUMISK	ALDER	2	21-02-2023	05-03-2023	18,9		
HUPEST	ALDER	2	17-02-2023	10-03-2023	25,3		
HUSALG	ALDER	2	18-02-2023	17-03-2023	25,3		
HUSZE2	ALDER	2	17-02-2023	02-03-2023	35,6		
LTSIAU	ALDER	2	19-03-2023	11-04-2023	46		
LTVILN	ALDER	2	14-03-2023	25-03-2023	138,5		
MONTREAL	ALDER	2	09-04-2023	11-05-2023	35,8		
NLLEID	ALDER	2	08-02-2023	23-03-2023	133,4		
PLBIAL	ALDER	2	10-03-2023	24-03-2023	93,5		
PLBYDG	ALDER	2	17-02-2023	16-04-2023	24,3		
PLCRAC	ALDER	2	26-02-2023	14-03-2023	33,5		
PLKATO	ALDER	2	10-03-2023	14-03-2023	44,8		
PLLODZ	ALDER	2	03-03-2023	20-03-2023	54		
PLLUBL	ALDER	2	18-02-2023	31-03-2023	18,9	PLPTRY	completely missing
PLPTRY	ALDER	2	18-02-2023	31-03-2023	18,9		
PLSZCZ	ALDER	2	17-02-2023	16-04-2023	24,3	PLBYDG	completely missing
PLWROC	ALDER	2	01-03-2023	14-03-2023	46,5		
QUEBEC	ALDER	2	13-04-2023	09-05-2023	20,4		
SKBRAT	ALDER	2	17-02-2023	11-03-2023	43,2		
SKNITR	ALDER	2	17-02-2023	11-03-2023	43,2	SKBRAT	completely missing
ATWIEN	BIRCH	1	28-03-2022	03-05-2022	367,9		LOCF
CZTRIN	BIRCH	1	14-04-2022	15-05-2022	378,4		
DEAACH	BIRCH	1	23-03-2022	26-04-2022	260,5	DEMOEN	completely missing
DEBOCH	BIRCH	1	23-03-2022	29-04-2022	323,5		
DEBORS	BIRCH	1	16-04-2022	11-05-2022	324,8		
DEDRES	BIRCH	1	06-04-2022	11-05-2022	463,6		
DELEVE	BIRCH	1	22-03-2022	24-04-2022	221,4		
DELOEW	BIRCH	1	28-03-2022	09-05-2022	132,1		
DEMARB	BIRCH	1	09-04-2022	11-05-2022	556,8		
DEMOEN	BIRCH	1	23-03-2022	26-04-2022	260,5		
DKCOPE	BIRCH	1	27-04-2022	30-04-2022	41		

FRSTRA	BIRCH	1	24-03-2022	04-05-2022	228,2		
HUGYOE	BIRCH	1	28-03-2022	03-05-2022	185,2		
HUMISK	BIRCH	1	05-04-2022	14-05-2022	250,1		
HUPEST	BIRCH	1	26-03-2022	10-05-2022	175,5		
HUSALG	BIRCH	1	07-04-2022	12-05-2022	257,3		
HUSZE2	BIRCH	1	29-03-2022	14-05-2022	131,4		
LTSIAU	BIRCH	1	21-04-2022	24-05-2022	560,2		
LTVILN	BIRCH	1	26-04-2022	24-05-2022	389,2		
MONTREAL	BIRCH	1	08-05-2022	13-05-2022	150,9		
PLBYDG	BIRCH	1	13-04-2022	15-05-2022	1053,9		
PLCRAC	BIRCH	1	12-04-2022	13-05-2022	601		
PLKATO	BIRCH	1	08-04-2022	23-05-2022	1049,2		
PLLODZ	BIRCH	1	13-04-2022	14-05-2022	972,1		
PLLUBL	BIRCH	1	14-04-2022	13-05-2022	632,8		
PLPTRY	BIRCH	1	13-04-2022	14-05-2022	1002,3		
PLSZCZ	BIRCH	1	18-04-2022	03-05-2022	78,3		
QUEBEC	BIRCH	1	09-05-2022	14-05-2022	198,7		
RUMOSC	BIRCH	1	21-04-2022	13-05-2022			
SKBRAT	BIRCH	1	27-03-2022	12-05-2022	441,6		
ATWIEN	BIRCH	2	24-03-2023	24-04-2023	64,3		
BEBRUS	BIRCH	2	12-04-2023	01-05-2023	143,2	NLLEID	completely missing
BEMARC	BIRCH	2	02-04-2023	05-05-2023	329,1	DEMOEN	completely missing
CZTRIN	BIRCH	2	13-04-2023	06-05-2023	189,6		
DEBOCH	BIRCH	2	10-04-2023	05-05-2023	615,5		
DEDRES	BIRCH	2	17-04-2023	01-05-2023	68,2	DEMARB	partially missing
DELEVE	BIRCH	2	05-04-2023	14-04-2023	172,1		LOCF
DELIPP	BIRCH	2	17-04-2023	02-05-2023	212,9		
DELOEW	BIRCH	2	17-04-2023	05-05-2023	81,4		
DEMARB	BIRCH	2	17-04-2023	01-05-2023	68,2		
DEMOEN	BIRCH	2	02-04-2023	05-05-2023	329,1		
DEMUNC	BIRCH	2	21-04-2023	05-05-2023	158,5		
DKCOPE	BIRCH	2	19-04-2023	05-05-2023	248,4		
DKVIBO	BIRCH	2	20-04-2023	14-05-2023	250,4		
FRSTRA	BIRCH	2	22-03-2023	05-05-2023	80,4		
HUGYOE	BIRCH	2	23-03-2023	24-04-2023	80,8		
HUMISK	BIRCH	2	16-04-2023	26-04-2023	338,8		LOCF
HUPEST	BIRCH	2	24-03-2023	26-04-2023	151,4		
HUSALG	BIRCH	2	12-04-2023	24-04-2023	613,4		
HUSZE2	BIRCH	2	24-03-2023	24-04-2023	141,3		

LTSIAU	BIRCH	2	19-04-2023	17-05-2023	162,7		
LTVILN	BIRCH	2	18-04-2023	15-05-2023	880,5		
MONTREAL	BIRCH	2	28-04-2023	24-05-2023	195,5		
NLLEID	BIRCH	2	12-04-2023	01-05-2023	143,2		
PLBIAL	BIRCH	2	17-04-2023	07-05-2023	277,5		
PLBYDG	BIRCH	2	17-04-2023	06-05-2023	283,7		
PLCRAC	BIRCH	2	13-04-2023	04-05-2023	260,2		
PLLODZ	BIRCH	2	16-04-2023	06-05-2023	464,1		
PLLUBL	BIRCH	2	16-04-2023	07-05-2023	327,4	PLPTRY	completely missing
PLPTRY	BIRCH	2	16-04-2023	07-05-2023	327,4		
PLSZCZ	BIRCH	2	17-04-2023	06-05-2023	283,7	PLBYDG	completely missing
PLWROC	BIRCH	2	15-04-2023	02-05-2023	409,7		
QUEBEC	BIRCH	2	05-05-2023	29-05-2023	243		LOCF
SKBRAT	BIRCH	2	25-03-2023	24-04-2023	138		
SKNITR	BIRCH	2	25-03-2023	24-04-2023	138	SKBRAT	completely missing

ATWIEN	HAZEL	1	30-01-2022	17-03-2022	30		
CZTRIN	HAZEL	1	10-02-2022	23-03-2022	100,4		
DEAACAH	HAZEL	1	09-02-2022	21-02-2022	81,1		
DEBOCH	HAZEL	1	28-01-2022	15-02-2022	55,3		
DEBORS	HAZEL	1	27-01-2022	24-02-2022	25,1		
DEDRES	HAZEL	1	28-01-2022	19-02-2022	31,9		
DELEVE	HAZEL	1	12-02-2022	18-02-2022	26,3		
DELOEW	HAZEL	1	28-01-2022	14-03-2022	23,2		
DEMARB	HAZEL	1	27-01-2022	13-03-2022	20,4		
DEMOEN	HAZEL	1	31-12-2021	15-02-2022	14,4		
FRSTRA	HAZEL	1	02-01-2022	13-03-2022	71,4		
HUGYOE	HAZEL	1	02-02-2022	24-03-2022	21,8		
HUMISK	HAZEL	1	05-02-2022	28-03-2022	53,9		
HUPEST	HAZEL	1	29-01-2022	31-03-2022	41,8		
HUSALG	HAZEL	1	05-02-2022	03-04-2022	69,3		

HUSZE2	HAZEL	1	03-02-2022	31-03-2022	47,1		
LTSIAU	HAZEL	1	12-03-2022	28-03-2022	64,2		
LTVILN	HAZEL	1	15-03-2022	26-03-2022	65,7		
PLBYDG	HAZEL	1	07-02-2022	24-03-2022	20,7		
PLCRAC	HAZEL	1	09-02-2022	21-03-2022	49		
PLKATO	HAZEL	1	09-02-2022	21-03-2022	46,2		
PLLODZ	HAZEL	1	12-02-2022	22-03-2022	22,3		LOCF
PLLUBL	HAZEL	1	13-02-2022	24-03-2022	42,1		
PLPTRY	HAZEL	1	09-02-2022	24-03-2022	31,4		
PLSZCZ	HAZEL	1	28-01-2022	30-01-2022	20,7		
RUMOSC	HAZEL	1	18-03-2022	12-04-2022			
SKBRAT	HAZEL	1	02-02-2022	01-05-2022	21,5		
ATWIEN	HAZEL	2	16-02-2023	10-03-2023	19,4		
BEBRUS	HAZEL	2	06-01-2023	18-02-2023	6	NLLEID	completely missing
BEMARC	HAZEL	2	31-12-2022	12-04-2023	28,9	DEMOEN	completely missing
CZTRIN	HAZEL	2	11-01-2023	26-02-2023	29,5		
DEBOCH	HAZEL	2	05-01-2023	23-02-2023	58,1		
DEDRES	HAZEL	2	03-02-2023	02-03-2023	37,3		
DELEVE	HAZEL	2	05-01-2023	07-01-2023	29,3		
DELIPP	HAZEL	2	13-02-2023	27-02-2023	39,9		
DELOEW	HAZEL	2	15-02-2023	06-03-2023	42,7		
DEMARB	HAZEL	2	05-01-2023	12-03-2023	10,3		
DEMOEN	HAZEL	2	31-12-2022	12-04-2023	28,9		
DEMUNC	HAZEL	2	04-01-2023	10-03-2023	31,7		
DKCOPE	HAZEL	2	11-02-2023	21-02-2023	25,1		
FRSTRA	HAZEL	2	02-01-2023	10-03-2023	89,6		
HUGYOE	HAZEL	2	13-01-2023	21-02-2023	5,8		
HUMISK	HAZEL	2	17-02-2023	13-03-2023	29,3		LOCF
HUPEST	HAZEL	2	01-01-2023	16-03-2023	17,4		
HUSALG	HAZEL	2	27-01-2023	16-03-2023	22,1		
HUSZE2	HAZEL	2	07-01-2023	10-03-2023	14,5		
LTSIAU	HAZEL	2	19-03-2023	22-03-2023	43,7		
LTVILN	HAZEL	2	18-03-2023	24-03-2023	51,4		
NLLEID	HAZEL	2	06-01-2023	18-02-2023	6		
PLBYDG	HAZEL	2	10-01-2023	19-03-2023	14		
PLCRAC	HAZEL	2	10-01-2023	14-03-2023	11,3		
PLKATO	HAZEL	2	21-02-2023	19-03-2023	18,7		
PLLODZ	HAZEL	2	17-03-2023	19-03-2023	14,7		
PLLUBL	HAZEL	2	06-02-2023	15-03-2023	15,6	PLPTRY	completely missing

PLPTRY	HAZEL	2	06-02-2023	15-03-2023	15,6		
PLSZCZ	HAZEL	2	10-01-2023	19-03-2023	14	PLBYDG	completely missing
SKBRAT	HAZEL	2	17-02-2023	11-03-2023	25,6		
SKNITR	HAZEL	2	17-02-2023	11-03-2023	25,6	SKBRAT	completely missing
ATWIEN	OAK	1	24-04-2022	20-05-2022	134,2		
CZTRIN	OAK	1	02-05-2022	22-05-2022	84,9		
DEAACAH	OAK	1	14-04-2022	17-05-2022	253,3	DEMOEN	completely missing
DEBOCH	OAK	1	18-04-2022	14-05-2022	353,4		
DEBORS	OAK	1	01-05-2022	22-05-2022	786,7		
DEDRES	OAK	1	28-04-2022	11-05-2022	582,1		
DELEVE	OAK	1	14-04-2022	11-05-2022	193		
DELOEW	OAK	1	14-04-2022	13-05-2022	89,7		
DEMARB	OAK	1	03-05-2022	20-05-2022	430,1		
DEMOEN	OAK	1	14-04-2022	17-05-2022	253,3		
DKCOPE	OAK	1	11-05-2022	22-05-2022	60,5		
FRSTRA	OAK	1	13-04-2022	20-05-2022	136		
HUGYOE	OAK	1	30-04-2022	12-05-2022	32,2		
HUMISK	OAK	1	29-04-2022	22-05-2022	65,3		
HUPEST	OAK	1	24-04-2022	22-05-2022	91,3		
HUSALG	OAK	1	24-04-2022	23-05-2022	196,2		
HUSZE2	OAK	1	14-04-2022	19-05-2022	42,9		
LTSIAU	OAK	1	17-05-2022	28-05-2022	25,1		
LTVILN	OAK	1	19-05-2022	27-05-2022	40,4		
MONTREAL	OAK	1	13-05-2022	19-05-2022	32,6		LOCF
PLBYDG	OAK	1	28-04-2022	24-05-2022	74,9		
PLCRAC	OAK	1	28-04-2022	16-05-2022	101,2		
PLKATO	OAK	1	15-04-2022	21-05-2022	57,9		
PLLODZ	OAK	1	05-05-2022	21-05-2022	124,5		
PLLUBL	OAK	1	05-05-2022	21-05-2022	76,1		
PLPTRY	OAK	1	30-04-2022	23-05-2022	97,3		
PLSZCZ	OAK	1	07-05-2022	13-05-2022	24,3		
QUEBEC	OAK	1	18-05-2022	26-05-2022	94,2		
RUMOSC	OAK	1	07-05-2022	22-05-2022			
SKBRAT	OAK	1	25-03-2022	22-05-2022	115,4		
ATWIEN	OAK	2	21-04-2023	11-05-2023	39,5		
BEBRUS	OAK	2	03-05-2023	21-05-2023	46,1	NLLEID	completely missing
BEMARC	OAK	2	10-04-2023	21-05-2023	63,5	DEMOEN	completely missing
CZTRIN	OAK	2	11-05-2023	14-05-2023	29,8		
DEBOCH	OAK	2	09-04-2023	16-05-2023	89,2		

DEDRES	OAK	2	17-05-2023	25-05-2023	30,7	DEMARB	partially missing
DELEVE	OAK	2	25-04-2023	21-05-2023	83,7	DEMOEN	partially missing
DELIPP	OAK	2	28-04-2023	22-05-2023	112,1		LOCF
DELOEW	OAK	2	22-04-2023	10-05-2023	28,1		
DEMARB	OAK	2	17-05-2023	25-05-2023	30,7		
DEMOEN	OAK	2	10-04-2023	21-05-2023	63,5		
DEMUNC	OAK	2	03-05-2023	23-05-2023	33,1		
DKCOPE	OAK	2	10-05-2023	23-05-2023	27,5		
DKVIBO	OAK	2	12-05-2023	26-05-2023	91,8		
FRSTRA	OAK	2	23-03-2023	21-05-2023	31,9		
HUGYOE	OAK	2	22-04-2023	10-05-2023	12,4		
HUPEST	OAK	2	16-04-2023	09-05-2023	36,4		
HUSALG	OAK	2	28-04-2023	22-05-2023	76,7		
HUSZE2	OAK	2	11-04-2023	04-05-2023	55,7		
LTSIAU	OAK	2	11-05-2023	23-05-2023	39,7		
LTVILN	OAK	2	10-05-2023	16-05-2023	39,1		
MONTREAL	OAK	2	11-05-2023	22-05-2023	121,5		
NLLEID	OAK	2	03-05-2023	21-05-2023	46,1		
PLBYDG	OAK	2	23-04-2023	23-05-2023	18		
PLCRAC	OAK	2	23-04-2023	14-05-2023	49,1		
PLKATO	OAK	2	05-05-2023	18-05-2023	28,6		
PLLODZ	OAK	2	02-05-2023	18-05-2023	89,6		
PLLUBL	OAK	2	27-04-2023	23-05-2023	44,4	PLPTRY	completely missing
PLPTRY	OAK	2	27-04-2023	23-05-2023	44,4		
PLSZCZ	OAK	2	23-04-2023	23-05-2023	18	PLBYDG	completely missing
PLWROC	OAK	2	21-04-2023	18-05-2023	49,5		
QUEBEC	OAK	2	19-05-2023	29-05-2023	253,3		LOCF
SKBRAT	OAK	2	22-03-2023	11-05-2023	23,2		
SKNITR	OAK	2	22-03-2023	11-05-2023	23,2	SKBRAT	completely missing

Signature Page for VV-CLIN-003596 v1.0

Approval Task	[REDACTED]
	19-Sep-2023 14:05:01 GMT+0000
Approval Task	[REDACTED]
	19-Sep-2023 16:08:09 GMT+0000
Approval Task	[REDACTED]
	19-Sep-2023 17:49:39 GMT+0000
Approval Task	[REDACTED]
	19-Sep-2023 17:58:39 GMT+0000
Approval Task	[REDACTED]
	20-Sep-2023 06:04:11 GMT+0000

Signature Page for VV-CLIN-003596 v1.0
